## 22. Economic Burden to Subjects

Research Procedures	Number of Samples/Procedures	Responsible Party	
		Study	3 rd Party Payer or Participant
Biofeedback Device	1 device		
Smartphone Data	90 days		
Standard of Care Procedures	Number of Samples/Procedures	Responsible Party	
		Study	3 rd Party Payer or Participant
Clinic Visit	1		
Pelvic Floor Physical Therapy	4		
3 month follow up visit	1		
Transportation to Physical Therapy	0-4		
Transportation to Clinic visits	2		

There are no study related costs to the participant outside of what would be recommended for standard care. Whether enrolled in the biofeedback device or PFPT, participants will not be

**PROTOCOL TITLE: SQEASI: Systematized Quality Exercise Alternatives for Stress Incontinence**

billed for the study materials. The smartphone apps are free and the biofeedback device will be provided without cost, though the biofeedback smartphone app does use data to record the workout, so it is possible that the patient will use a small amount cell phone carrier data. As part of the study, we will not be offering to compensate participants for charges from their phone companies. They have already chosen to undergo conservative management of their SUI, and they will receive prior authorization from their 3rd party payers if randomized to PFPT, or they will have worked out financial assistance, if needed. These costs will be billed to their insurance provider and costs may range from copay only to full cost of treatment.

The PeriCoach© device and associated materials will be provided free of charge by the study to those randomized to PeriCoach©.

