## 5. Number of Subjects

The primary outcome of this study is improvement in incontinence quality of life as measured by the ICIQ-SF Questionnaire. We used the previously reported means and standard deviation for this questionnaire (3) from a prior RCT on biofeedback and pelvic floor exercises. We have powered the study based on a 4-point difference as significant between groups. This 4-point difference used for the power calculation is based on prior studies and the minimally important difference that has been previously established (4). To achieve power for this non-inferiority RCT demonstrating a difference between groups of less than 4 points we need 21 patients per group (biofeedback versus PFPT) to detect no difference with an alpha =0.05 and

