## PROTOCOL TITLE: *SQEASI: Systematized Quality Exercise Alternatives for Stress Incontinence*

with 80% power. Allowing for a dropout of 20% we will enroll at least 50 patients (or 25/group), but up to 75 total.

This is a not a multi-center study. Data will be housed at the Eubank clinic

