Randomization assignment will be generated by computer based randomization table and assigned by a research coordinator not otherwise involved in the study. Assignments will be kept in sealed opaque envelopes numbered sequentially. On the day of the patient's clinic visit, after signing consent and deciding to participate, the research coordinator will bring the next envelope in the sequence will be opened, randomizing the patient to PFPT or home biofeedback. The therapy allocation will then be carried out.

The biofeedback group will be given a PeriCoach® biofeedback device, which has a Bluetooth connection to a smartphone, free of charge. The smartphone application will be uploaded during the visit and linked to the device to ensure the patient understands how to

PROTOCOL TITLE: *SQEASI: Systematized Quality Exercise Alternatives for Stress Incontinence*

install the program. An information sheet with recommendation for exercise frequency will be given at the time of enrollment to provide recommendations for use. All participants will start as a beginner in the program and works up to a maintenance level. At the end we expect they will be doing 15 exercises, 3 times per day per manufacturer's instructions. 2 weeks following enrollment, these patients will be called to ensure they understand how device functions and are not having technical difficulties. When the patient returns for the 3 month follow up the smartphone app will be reviewed as the app records how often the patient performs the exercises. If that is not available, we will have the patient self-report her exercise frequency.

For patients randomized to physical therapy, PFPT will be scheduled for 4 sessions over 3 months, as is common practice for patients with SUI. These patients will receive instructions on how to engage their core, contract their vaginal muscles, as well as recommendations for home exercises to be performed for 3 sessions per day. The first session will be to establish the patient's baseline abilities with follow up sessions to reinforce instructions, performance of exercises and to ensure the patient is improving. Patient compliance of attending PT sessions will be recorded, as will the amount each patient spends in co-pays per session. After 3 months, regardless of the number of appointments the patient has attended, she will return for a follow up visit to assess how well she is doing.

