## **13. Data Analysis**

Data Analysis: Between and within group differences will be evaluated using Fisher's exact test for categorical variables and t-tests for continuous variables. If there are any baseline differences between groups, a multivariate analysis will determine the contribution of these differences to observed differences (if any) between groups.

Power Analysis: Power analysis was performed based on previously reported means and standard deviation for the ICIQ-SF questionnaire. The primary outcome of this study is improvement in incontinence quality of life as measured by the ICIQ-SF Questionnaire. We used the previously reported means and standard deviation for this questionnaire (10) from a prior RCT on biofeedback and pelvic floor exercises. We have assumed a change score of greater than 4 points to be significant between groups based on prior studies and the minimally important difference that has been previously established (11). To achieve significance for a non-inferiority study using these assumptions we would need 42 patients, 21 per group to detect this difference with alpha =0.05 and with 80% power. To allow for a dropout of 20% we will enroll at least 50 patients, but up to 75 to account for participants who are lost to follow up.

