## **15. Withdrawal of Subjects**

Any participant may withdraw from the study at any time without penalty and will continue to receive the clinical standard of care. A subject may be withdrawn from the study without her consent at the discretion of the physician and study staff if they believe she no longer meets study inclusion criteria or if she meets exclusion criteria, or if they believe that it is not in her best interest to continue study participation. Investigators may withdraw a subject if the subject is not following the study protocol. If a woman is withdrawn from the study either at her own discretion or that of the research staff, she may continue with conservative or surgical management of her SUI in the usual fashion.

To minimize withdrawal from the study, patients will be randomized just after deciding on non-surgical management and signing consent. According to the 2010 CONSORT guidelines, we will analyze all participants assessed for eligibility within the study. We will document reasons for withdrawal from the study including failure to meet eligibility criteria or participant declining enrollment into the study. We will report eligibility criteria not met or reasons for declining participation in the study. The withdrawal procedure is clearly documented in the study consent.

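### PFPT is billed to the payer or participant while the device is free, and no ICIQ-SF analysis protects the non-inferiority claim if PFPT is under-delivered

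*Combined protocol and SAP*

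**What the plan says.** **Cost and timing.** The table in Section 22 assigns the four PFPT sessions, and transport to them, to the third-party payer or the participant, and the device to the study. The text adds: "These costs will be billed to their insurance provider and costs may range from copay only to full cost of treatment". Prior authorization is to come from third "party payers if randomized to PFPT, or they will have worked out financial assistance, if needed". Under Section 15, "patients will be randomized just after deciding on non-surgical management and signing consent". Section 8 has the device handed over in clinic, with staff helping to set it up.

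**Eligibility.** Section 4 requires willingness to attend four PFPT visits and excludes women who decline or cannot return for them. It does not mention coverage or affordability.

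**Follow-up.** Section 12 states: "After 3 months, regardless of the number of appointments the patient has attended, she will return for a follow up visit". It also provides that, if PFPT starts late, the visit falls 3 months after the first PT appointment.

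**Adherence data.** Section 12 records PT attendance and copays. In the device arm it records exercise frequency from the app or, failing that, by self-report. Section 7 lists compliance between groups as an exploratory endpoint.

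**Analysis.** Section 13 gives t-tests and Fisher's exact tests. It defines no analysis set, no minimum exposure and no rule for a woman who never starts PFPT. Section 15 cites CONSORT and speaks of analysing everyone assessed for eligibility. That group includes women who were never randomized, so the sentence cannot serve as the analysis set.

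**The concern.** The study removes the cost barrier in one arm and leaves it in the other. Sections 1 and 2 themselves name copays, cost and travel as obstacles to PFPT, so missed sessions for these reasons can be foreseen.

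In a superiority trial, an under-delivered control would exaggerate the benefit of the new treatment. In this trial it narrows or hides a deficit. Each woman in the PFPT arm who receives little PFPT lowers that arm's mean improvement and moves the observed difference towards zero, which is where non-inferiority is declared. At stake is whether a finding within 4 points means that the device performs like PFPT, or only like PFPT that was partly not received. As written, Section 13 gives a reader no planned result that separates the two.

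**Working it through.** **1. The plan's own figure.** Section 5: "demonstrating a difference between groups of less than 4 points we need 21 patients per group". Section 13: "to detect this difference with alpha =0.05 and with 80% power". On the SD, Section 5 says only: "We used the previously reported means and standard deviation for this questionnaire". Neither the SD nor the sidedness of alpha is given, so 21 per group can be neither confirmed nor refuted. With a true difference of zero,

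n per group = 2 × SD² × (z₁₋α + z₀.₈₀)² / 4²

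Solving for the SD that returns 21:

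- One-sided 0.025 (two-sided 0.05): SD about 4.51 to 4.63. Check: 2 × 4.62² × (1.960 + 0.842)² / 16 = 20.9, which rounds up to 21.
- One-sided 0.05: SD about 5.09 to 5.21.

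**2. Dilution model.** Let f be the share of the PFPT arm that receives no PFPT but is still analysed, and L the ICIQ-SF improvement that such a woman loses. The documents give neither, so both are assumptions. Take a device that is truly 4 points worse than delivered PFPT, so that non-inferiority to delivered PFPT is false.

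- Expected observed difference = 4 − f × L
- SE = SD × √(2/21) = 4.62 × 0.3086 = 1.426
- Chance of claiming non-inferiority = Φ(f × L / SE − z₁₋α)

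**3. Worked case.** With f = 20% and one-sided 0.025:

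- L = 2: shift 0.4, difference 3.6; Φ(0.281 − 1.960) = 4.7%
- L = 4: shift 0.8, difference 3.2; Φ(0.561 − 1.960) = 8.1%
- L = 6: shift 1.2, difference 2.8; Φ(0.842 − 1.960) = 13.2%

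**4. Range.** Chance of a false claim, 21 per group, SD 4.62, one-sided 0.025:

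| f | L = 2 | L = 4 | L = 6 |
|---|---|---|---|
| 0% | 2.5% | 2.5% | 2.5% |
| 10% | 3.4% | 4.7% | 6.2% |
| 20% | 4.7% | 8.1% | 13.2% |
| 30% | 6.2% | 13.2% | 24.3% |

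With one-sided 0.05 and SD 5.21, the row for f = 20% is 8.1%, 12.6% and 18.4%, against 5.0% nominal.

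**5. What the model leaves out.** It assumes that every non-attender is followed up and analysed, and that device use is complete. The documents guarantee neither.

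**The case against.** A reader might infer three stronger things from these sections. The documents do not support them.

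- *Under-delivery is built into the design.* No refusal, non-start or attendance rate is given. Section 4 excludes women unable to return for PT and does not limit inability to non-financial reasons. An authorization delay alone need not shorten treatment, because the follow-up visit moves with the first PT appointment.
- *Cost is settled only after randomization.* That is clear only for payer authorization. The wording on financial assistance can equally mean that it is arranged beforehand.
- *The recorded attendance is never used.* It feeds the exploratory compliance comparison. What is missing is narrower: no ICIQ-SF analysis takes delivery into account.

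The direction of bias is not certain either. Section 15 lets investigators withdraw women who do not follow the protocol, and a woman who never starts PFPT has no first appointment from which to date her visit. She may be missing rather than diluting the arm, and selective missing data have no fixed direction. Poor device use would push the other way. Section 8 has every woman taught a correct contraction at the clinic examination, which argues for a smaller L.

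The strongest objection is that payer-billed PFPT is standard care. If the question is how the two options compare as patients actually obtain them, some missed sessions belong to the comparison, and a claim made after dilution is not false in that sense. Part of this stands. However, the protocol does not say that this is its question, the free device is a feature of the study, and cost already has its own aim (Aim 2), separate from the quality-of-life comparison in Aim 1. What remains is that the plan neither states which comparison it wants nor provides a result that would show whether the answer depends on delivery.

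**Conclusion.** The point holds as a foreseeable and unprotected risk. Billing differs by arm, PFPT authorization depends on allocation, outcomes are taken whatever was attended, and no planned ICIQ-SF analysis reflects delivery. If PFPT is under-delivered and those women are analysed as randomized, the comparison leans towards non-inferiority.

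The size cannot be fixed from the documents. The 5% to 13% range applies to one illustrative setting: 20% attending nothing, all of them analysed, a true 4-point deficit, an SD back-solved from the plan's 21 per group, and a 2- to 6-point loss. It shows that modest non-attendance could double the nominal error rate or raise it about fivefold (4.7/2.5 = 1.9; 13.2/2.5 = 5.3). It does not predict that this will happen.

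**What to change.** **Section 13**

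- Keep the all-randomized ICIQ-SF comparison as primary.
- Pre-specify a supportive analysis of the same difference in adherent women. Define the criterion before data review and apply one in both arms: PFPT sessions attended, and app-recorded or self-reported device exercise. Restricting the PFPT arm alone would compare selected women with all device users.
- State how women who never start PFPT are followed up, from which date, and how they are analysed. Reconcile this with the discretionary withdrawal in Section 15.
- Report both results against the 4-point margin, and do not call the non-inferiority claim robust if they disagree.

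**Section 22**

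- Clarify whether financial assistance is settled before or after randomization.

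**Cost.** One extra analysis of data already collected. It will be less precise than the primary, with fewer than about 21 per group. It is open to selection, because adherent women may differ from the rest and adherence is measured differently in each arm. It therefore supports the primary analysis and does not replace it.

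Confirming coverage before the envelope is opened is optional. Section 25 already lets women join at a later visit, but the step would delay randomization for some and might exclude the access-limited women whom Section 2 describes.

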**23. Compensation**

For completion of the study, each patient will be compensated with a merchant gift card worth \$50 total. They will receive a \$10 gift card at their initial study visit (enrollment) and \$40 gift card at their 3-month follow-up visit in the form of Target gift cards. This payment is reasonable compensation for the inconvenience of participating in a research study due to the additional time the study questionnaires will require from the participant.

**24. Compensation for Research-Related Injury**

If participants are injured or become sick as a result of this study, UNMHSC will provide emergency treatment at the study participant's cost. No commitment is made by the University of New Mexico Health Sciences Center to provide free medical care or money for injuries to participants of the study. Reimbursement for treatment for all related costs of care will be sought from the participant insurer, managed care plan, or other benefits program. The participant will be responsible for any associated co-payments or deductibles required by the insurance. Participants will be encouraged to report any illness or injury they believe to be related to the study to the investigator or research staff. Participants will be given telephone contact information for the urogynecology office for the purpose of asking any questions or stating any concerns about the study or treatment as a research subject. They may also be directed toward the HRPO. This language will be stated in the written consent document, and reviewed during the informed consent process

**25. Consent Process**

Patients will be approached about the research study at the urogynecology clinic at UNM Eubank and at SRMC during a discussion for the management of SUI. Each patient undergoes counseling in a private room with a closed door to ensure privacy. The physicians in the

**PROTOCOL TITLE: SQEASI: Systematized Quality Exercise Alternatives for Stress Incontinence**

urogynecology division and research staff will be able to obtain consent after the participants have been counseled about their condition. Our division routinely treats this condition and are highly qualified to counsel patient regarding the risks, benefits, alternatives for the treatment. Those recruited will have already decided to undergo conservative management of SUI. Hence, they will not be coerced into performance of any “extra” treatments. Additionally, care will not be withheld if they decide not to participate.

The patients who would like to participate in the study will be consented during their new or return visit in the urogynecology clinic. They will have these multiple opportunities to ask any questions that they may have, and they will also be provided with the clinic’s contact information to get in touch with research investigators to address any additional questions or concerns. If they decide to participate at the next visit, they will be allowed to join as long as no anti-incontinence procedure or PFPT has taken place in the interim.

Subjects will be reassured that participation is completely voluntary and does not affect their treatment, their relationship with their providers, or the university to minimize the possibility of coercion or undue influence. The patients will be asked that they understand the opportunity to participate and their complete freedom to decline. This will also be asked if they understand and if they have any questions. There is no minimum time period needed between informing the patient of the study and time of consent. Subjects will be encouraged to take as much time as they need.

This study will obtain HIPAA authorization prior to enrollment. HIPAA authorization is imbedded within the study consent form, which will be reviewed with all participants by the physician or research staff obtaining consent. Specific information that will be obtained includes prior medical history, surgical history, reproductive health history including child bearing, drug allergies, age, and ethnicity. This information will be obtained by health care providers, not research coordinators, as deemed necessary for a more complete and accurate medical history of the patient.

The HIPAA form is included in the consent attached.

***Subjects not fluent in English***

Spanish speaking patients will not be included in the study as the required Smartphone application is not available in Spanish. We do not anticipate enrolling subjects who have limited fluency in English.

***Cognitively Impaired Adults/Adults Unable to Consent/Use of a Legally Authorized Representative***

NA. Cognitively impaired subjects will not be included in this study.

***Subjects who are not yet adults (infants, children, teenagers)***

NA. Only subjects  $\geq 18$  years of age will be included in this study.

***Waiver or Alteration of Consent Process (consent will not be obtained, required element of consent will not be included, or one or more required elements of consent will be altered)***

NA. There will be no waiver or alteration of the consent process.

**26. Documentation of Consent**

We plan to document consent, and the Consent form is attached. We do not plan on collecting/storing tissue samples.

**27. Study Test Results/Incidental Findings**

We do not intend to share study test or procedure results with study participants. Additionally, we do not anticipate that the research being conducted will result in incidental findings. Every patient will receive the practice's standard of care regarding workup of SUI, which may include different laboratory tests, urine culture or urodynamic testing if unclear cause of incontinence, or imaging studies, as determined by their other active medical issues. These results are not directly a part of the research being conducted and will hence be disclosed to the patient. They will not, however, affect randomization.

**28. Sharing Study Progress or Results with Subjects**

We do not intend to share study progress with participants while the study is underway as not to introduce bias. We do not intend to seek out study participants to disseminate information once the study is complete. Women who are interested in the results will be provided the information where to read the manuscript once it is published. Study results for individual participants will not be shared.

**29. Inclusion of Vulnerable Populations**

There will not be any vulnerable populations included in this study. Those electing for treatment of SUI will not be coerced into doing so, nor will they be coerced into participating in this trial.

**30. Community-Based Participatory Research**

N/A. There will be no involvement of the community in this research.

### **31. Research Involving American Indian/Native Populations**

NA. This research does not specifically target this population. If a American Indian woman is a candidate for this study she will be offered participation

### **32. Transnational Research**

NA. This study is not transnational.

### **33. Drugs or Devices**

The PeriCoach© biofeedback device will be used to measure provide immediate patient feedback while performing the exercises at home. The device should be washed at home between uses, which will be discussed with patients at the visit. The device has already been tested and validated for measuring pelvic floor contractions and is FDA approved, hence, its safety is not being evaluated in this study.

The company PeriCoach© is in the process of changing manufacturers. As such they have added a sticker to the outside of the PeriCoach© box that state "investigational use only." This is still the same FDA approved device the sticker is intended to prevent resale of the device as it is not currently available for wholesale while they switch manufacturers.

The FDA letter is attached.

